A Pilot Randomized Controlled Trial Testing the Acceptability and Feasibility of a Pediatric Interactive Relational Agent (PIRA) vs. Standard Preoperative Education

NCT#: 04586569

Document Date: 01/26/2022

Title: A Pilot Randomized Controlled Trial Testing the Acceptability and Feasibility of a Pediatric Interactive Relational Agent (PIRA) vs. Standard Preoperative Education

A. Specific Aims/Objectives

The purpose of this study is to determine the feasibility and acceptability of enhanced preoperative education using a Pediatric Interactive Relational Agent (PIRA), designed for children ages 4 through 10 years and their families, compared to the standard preoperative education currently provided. Specifically, the study aims are to evaluate the following: 1. Parental/Child PIRA access and utilization, 2. Parental satisfaction and encountered issues with the PIRA, and 3. Differences in parental preoperative anxiety, child preoperative anxiety, and child experience with emergence from anesthesia between the PIRA and control group.

B. Background and Significance

Surgery and anesthesia can be extremely stressful experiences for the pediatric population. Children, in particular, may respond negatively to the impact of the experience. Kain (1999) and Kotiniemi et al. (1997) found that more than 60% of children experienced anxiety during preoperative waiting, increasing the risk of numerous psychological stressors such as postoperative delirium and agitation. Additionally, they found sleep and eating disorders, separation anxiety, temper tantrums, and aggressive behaviors lasting up to 2 weeks, 6 months, and 1 year in 50%, 20%, and 7% of pediatric patients, respectively (Yuki & Daaboul, 2011). The negative impact of stress in children can result in short and long-term sequelae (examples as mentioned above), a regression of the child's emotional and behavioral development, delay of hospital discharge, and decreased overall parental satisfaction. Likewise, Stargatt et al. (2006)

and Bevan et al. (1990) demonstrated that parental anxieties can have a negative influence over the child's postoperative behavioral outcomes.

Anecdotally, parents frequently report a lack of understanding or a plan for how to address the idea of surgery and anesthesia to their child. This has been especially problematic in school-age children, who may lack the ability to anticipate and comprehend the necessary issues, solutions, and consequences. Evidence supports the benefits of enhanced preoperative education for pediatric patients and families. This, coupled with the lack of developed interactive agents preparing the pediatric patient and family for the perioperative anesthesia experience, demonstrated a need for the creation of such tools. This PIRA was developed by perioperative clinical experts, including perioperative Registered Nurses (RNs), Certified Registered Nurse Anesthetists (CRNAs), Physician Anesthesiologists, and Child Life Specialists (CLS) all with greater than two years' clinical experience, in addition to nonmedical parents. Piloting this intervention in a randomized controlled trial (RCT) to determine its impact on pediatric and parental anxiety, satisfaction, likelihood to recommend to others, and emergence from anesthesia, is critical for successful implementation and potential future iterations.

Given the large anesthetic volume at Boston Children's Hospital (BCH), this PIRA intervention has the ability to positively impact tens of thousands of patients and families to adjunct the preoperative process to reduce anxiety, provide knowledge in regards to the perioperative anesthesia experience (preoperative, intraoperative and postoperative), enhance communication between the child and parent (encourage questions, explanations as it relates to the perioperative experience), prevent post-operative maladaptive behavior (POMB), and increase parental satisfaction with the perioperative experience. Testing these potential benefits while adjusting the PIRA based on user feedback is essential for maximizing the impact and

dissemination of the tool. Moving forward, expanding the PIRA to include additional languages, a wider developmental age range, different anesthetic options other than general anesthesia, and including anesthetic locations outside of the operating room—such as radiology, procedural rooms, wound care, gastroenterology, or the emergency department—will further enhance these benefits and include more families.

C. Preliminary Studies

Perioperative programs designed to decrease patient and parental anxieties and set expectations are paramount to positive medical and psychosocial interactions, satisfaction, and outcomes. Numerous perioperative program publications and randomized controlled trials (RCTs) show interactive preoperative information reduces parental and patient anxiety (Batuman et al., 2016; Bartik & Toruner, 2017; Cassidy et al. 1999; Chartrand et al., 2016; Felder-Puig et al., 2003; Fortier et al., 2015; Hilly et al., 2015; Kain et al., 1996; Kain et al., 1995; Kain et al., 2007; Kassai et al., 2016; Liguori et al., 2016; Maclaren & Kain, 2007; McEwen et al., 2007; O’Conner-Von, 2008; Perry et al., 2012; Vaezzadeh et al., 2011; Wakimizu, 2015; Wantanakorn et al., 2018). Others have demonstrated that education and information programs decrease emotional trauma and regressive behaviors such as bedwetting, night terrors, and medical anxiety (Bartik & Toruner, 2017; Batuman et al., 2016; Hilly et al., 2015; Kain et al., 2007). RCTs have even found lower pain scores and opioid requirements in pediatric patients who participated in a preoperative information program (Chartrand et al., 2016; Kain et al., 2007). Furthermore, a systematic review of RCTs using media-based interventions for preoperative education found a parental desire for more education. This systematic review reported a statistically significant reduction in anxiety and an increase in knowledge after the interventions (Lee et al., 2003).

In adults, educational interactive videos, also called conversational or relational agents (Trinh et al., 2017), which include user participation and feedback have shown a significant reduction in preoperative anxiety (Ryu et al., 2018; Tou et al., 2012; Hoybye et al., 2016), increased satisfaction (Narimatsu et al., 2011), increased knowledge, and a shorter anesthetic interview, potentially indicating a greater understanding of the anesthetic plan, process, and risks (Kakinuma et al., 2011). In pediatrics, there are no such tested educational interactive relational agents, avatars, or animated videos for surgery or anesthesia.

Using an e-Delphi method to determine important topics to include in such a relational agent, in conjunction with a multidisciplinary team to develop age appropriate dialogue and content, a Pediatric Interactive Relational Agent (PIRA) was created. This PIRA, developed at BCH and programmed with a team at Northeastern University, is the first known relational agent specifically targeting pediatric patients ages 4 through 10 years old and their families, to educate them about anesthesia and the perioperative process prior to their surgical date.

D. Design and Methods

(1) Study Design

This study is a pilot 1:1 randomized trial with one control group and one intervention group. Children age 4 through 10 years and their parents will be randomized to receive the PIRA versus the standard education prior to Otorhinolaryngology (ORL) or Urology surgery. For the purpose of this protocol, “parents” refers to the biological or legally adopted parents or legal guardians. Using surveys, assessments, and data we collect from the medical record and PIRA, we will look at PIRA access and utilization, parental satisfaction and encountered issues with

PIRA, and differences in parental and child preoperative anxiety as well as child emergence agitation between the intervention and control groups.

(2) Patient Selection and Inclusion/Exclusion Criteria

We plan to enroll parents and their children, ages 4 through 10 years old, who are undergoing general anesthesia and elective, outpatient ORL or Urology surgery at BCH Waltham. Children will be American Society of Anesthesiology (ASA) physical status I or II. Parents must be at least 18 years of age or older. Since the study PIRA is currently only available in the English language, both parents and their children must be fluent in English in order to understand and interact with the PIRA.

Parents without reliable internet access to the Google Chrome browser through a tablet or computer, parents of children with diagnosed developmental delays, parents who have children who have had previous surgical history under general anesthesia, and parents of children involved in other anesthesia-related studies at BCH will be excluded for this study. A prior surgery or procedure performed under local anesthesia or without anesthesia (e.g. newborn circumcision, frenulotomy, or newborn Achilles tenotomy), would not exclude the participant. These exclusion criteria will be assessed during the consent phone call.

(3) Description of Study Treatments or Exposures/Predictors

Families that agree to participate in the study will be assigned a number (either one or two) from a random number generator. This will determine whether they are assigned to the PIRA (intervention) group or to the standard education (control) group.

Participants (children and their parents) will not be blinded to the study group (they will know if they received the PIRA). On the day of surgery, the research team member observing enrolled children for signs of anxiety in the preoperative area and the PACU nurse observing the children as they awaken from anesthesia post-operatively will be blinded to group assignment; they will not know, nor will they ask families, about their preoperative education experience.

Intervention Group: If assigned to the intervention group, families will receive access to the PIRA for a minimum of two days in addition to the standard of care pre-op education provided for all families (described below for the control group). The child's first name and age will be entered into the PIRA's enrollment page so that the tool can address the child by name and educate them in an age-appropriate manner. After an account has been created, an email containing instructions on the purpose of PIRA and how to use the program (Appendix A) will be sent to the email address provided by the family from a research team member at a BCH. Included in this email will be a hyperlink to access the PIRA, as well as a unique username and password for families to log in. Once enrolled, the PIRA will be accessible to the family as often and for as long as desired up to 10 days prior to the scheduled surgery. Parents will receive a reminder email a few days prior to their child's surgical date prompting them to log-in and complete the PIRA with their child at least once before the procedure. The parents will be encouraged to reach out to the Principal Investigator at any time if they have difficulty accessing the PIRA or if questions arise regarding the educational content within the program.

Control group: Participants assigned to the control group will receive the standard of care preoperative education at BCH Waltham. These participants will not receive any

additional preoperative educational materials or resources other than what is currently provided by their care team. This usually includes a routine phone call, text, or email from a pre-operative staff member within a few days of the child's scheduled procedure to provide basic information about fasting, when to arrive at the hospital, and anything additional that needs to be done prior to the procedure (e.g. COVID-19 testing), when applicable. Any specific information about the anesthetic will be deferred to the anesthesia team for the surgical day, per usual.

In both the intervention and control groups, if parents specifically request additional information to prepare for surgery, pre-op staff may send them the "Social Story" developed by the Autism Spectrum Center, Child Life Services, and Waltham Surgical Services. This document provides an age-appropriate step-by-step guide as to what to do and what to expect on the day of surgery.

On the day of surgery, all parents participating in the study, regardless of group assignment, will receive surveys to complete in the pre-operative holding area via REDCap®. The surveys will be given to the parent who consented to the study. If both parents are present, and both consented to the study, they will both receive surveys to complete. A research staff member trained for reliability and blinded to the study arm will assess the child for signs of anxiety in the pre-op holding area.

For both groups, once the surgical procedure is complete, and the child has gone to the PACU, Emergence Agitation/Delirium will be assessed per standard of care at Waltham by the bedside PACU nurse using the Pediatric Agitation Emergence Delirium Scale (PAED). The

research team will collect this PAED information retrospectively from the child's electronic medical record.

(4) Definition of Primary and Secondary Outcomes/Endpoints:

See Table 1 for Summary of Outcomes/Measures

Patient Demographics

Parental age, gender, ethnicity, and highest education level achieved will be collected as part of the REDCap® preoperative survey to better understand the pilot group and educational needs (Appendix B).

Primary Outcomes

Parental Utilization:

- *When provided with the opportunity to obtain more information as it relates to the perioperative experience, do parents and their children use the tool?*
- *How many times did they access the tool and for how long?*
- *Were there any barriers to accessing the PIRA tool?*

If there were problems surrounding the accessibility, content, language, or any other system issues, this will affect utilization and the PIRAs future potential impact.

Regardless of the medium, materials, or content provided, no preoperative educational program can be successful and sustainable unless readily adopted and utilized by parents and children. As such, a primary outcome will evaluate whether families actually viewed the materials, with whom, and how much time they spent with the PIRA.

Parental Perceived Impact and Impressions:

- *Did parents find the tool subjectively helpful?*
- *What improvements or changes in content or language would they consider?*
- *Would parents recommend the PIRA to future families?*

Identifying parental perceived benefits or drawbacks to the PIRA may elucidate the familial interactions and how they feel about their educational experience in a different way than anxiety or other objective data. Similarly, given the novel nature of the PIRA, it is important to identify any educational gaps and potential for future topics and educational needs. If parents believe the PIRA improved their preoperative experience, it could be useful for future families.

Secondary Outcomes

Child Anxiety in Preoperative Waiting:

As discussed, more than 60% of pediatric patients have been found to suffer from anxiety in the preoperative period. The effects of anxiety may have behavioral sequelae, or Postoperative Maladaptive Behaviors (POMB), which can last up to a year or longer. Therefore, reducing anxiety levels should be a priority of any educational tool for pediatrics. Numerous randomized control trials have demonstrated decreased child anxiety in preoperative waiting for those patients who participated in preoperative educational programs including videos, tours, apps, games, and books. *Is there a similar difference in the control and intervention groups' preoperative anxiety with this PIRA intervention?*

Parental Anxiety in Preoperative Waiting:

In several cited studies, parental anxiety directly correlates with the pediatric patient's anxiety. Thus limiting or reducing parental anxiety is an important part of a preoperative education intervention. *Does improved communication and education decrease parental anxiety?* An intervention which serves to improve communication between the parent/child as well as the parent/anesthesia provider AND reduce parental anxiety would perhaps provide significant benefits.

Emergence from Anesthesia: Presence or absence of emergence agitation/delirium (ED):

Depending on the study, ED has an incidence between 10-80%, with most studies showing 30-50% of children having ED after a general anesthetic (Przybylo et al., 2003; Ringblom et al., 2018). ED can be extremely distressing for parents, delay discharge from post-anesthesia care unit (PACU), can result in injury to the patient or staff (due to uncontrolled flailing, kicking, punching), and can also potentially result in the unintentional dislodgement of intravenous catheters or other tubes (e.g. nasogastric, gastrostomy, chest, endotracheal tubes). Data have shown a reduction in ED incidence with the use of preoperative education programs (Kain et al., 2004). *Is there any effect on the incidence of ED for children who have more interactive preoperative education, such as PIRA, compared to standard information?*

(5) Data Collection Methods, Assessments, Interventions and Schedule

On the day of the surgical procedure, participating parents in both the PIRA and the control groups will receive the same in-person surveys in the preoperative holding area. Surveys will be administered via REDCap® and completed on iPads which have been given to the

parents by a member of the research team (Appendix B). In both groups, the parent(s) who consented to the study and there on the day of surgery will be given the surveys.

The surveys will have no identifying questions and will be automatically uploaded to REDCap®. They will be accessible only to members of the research team. Children will not be asked to complete any surveys but will be observed in the pre-op holding area by a member of the research team and in the PACU by a PACU nurse, as per standard of care at BCH Waltham. Both will have been trained for reliability in conducting the study-specific assessment tools.

Pediatric Anesthesia Emergence Delirium (PAED) scores will be collected retrospectively from the child's electronic medical record. All data collected will be de-identified and presented or published in aggregate. The research team will provide a finished copy of the manuscript upon request.

Primary Outcomes Data

Parental Utilization:

The amount of time spent using the PIRA and the number of times the PIRA was accessed will be able to be collected via the program itself, stored on a secure Northeastern University Server, and will be accessible only to the study team. Each click of the mouse a user makes in the system will be timestamped and saved on the database. This information will be de-identified. Additionally, the parental survey administered by the research team member in the preoperative holding area will obtain self-reported data on PIRA access and time spent using the tool (Appendix B).

Parental perceived impact and impressions:

This outcome will be assessed in the same survey (Appendix B) as Parental Utilization. The survey will have no identifying questions and will be automatically uploaded to REDCap®, accessible only to members of the research team. Any data will be de-identified and presented in aggregate.

Secondary Outcomes Data

Child Anxiety in Preoperative Waiting:

Child anxiety will be assessed using the modified Yale Preoperative Anxiety Scale (mYPAS), an observational state anxiety measure for children containing 27 items in five categories (activity, emotional expressivity, state of arousal, vocalization, and use of parents). See Figure 1. The mYPAS has been validated for measuring childrens' anxiety (Kain et al., 1995; Kain et al., 1997). Members of the research team who will administer the mYPAS for this study will be trained for reliability. mYPAS scores range from 22.5 to 100, with higher scores indicating more anxiety.

Parental Anxiety in Preoperative Waiting:

Parental anxiety will be assessed using the State-Trait Anxiety Inventory (STAI). See Figure 2. This self-report anxiety instrument contains two separate 20-item subscales that measure trait (baseline) and state (situational) anxiety (Spielberger, 1973; Spielberger, 1983; Spielberger, 1989) This survey will take place in the preoperative holding area and will be administered in conjunction with the previous utilization/recommendation survey (Appendix B). The STAI is scored from 20-80, with higher scores indicating more anxiety.

Emergence from Anesthesia: Presence or absence of emergence agitation/delirium

(ED):

To determine any effect this PIRA may have on ED, the PACU RN assigned to care for the given patient will assess emergence upon patient arrival to PACU using the PAED scale. See Figure 3 for PAED Scale. The PAED is a routine assessment conducted by PACU RNs at Waltham for all post-operative pediatric patients upon emergence from anesthesia. A member of the research team will retrospectively extract the PAED score from the patient's chart. The PAED scale measures five behaviors, each rated on a five-point scale of zero to four. The scores are summed for total scale score up to a maximum value of 20 (Sikich & Lerman, 2004). An assessment of the internal consistency and reliability of the PAED scale validated it for assessing ED in children recovering from general anesthesia (Ringblom et al., 2018). A PAED ≥ 10 yields 64 percent sensitivity and 86 percent specificity (Sickich & Lerman, 2004), and a score of >12 yields 100 percent sensitivity and 94.5 percent specificity for the diagnosis of ED (Bajwa et al., 2010). For use in this study, ED will be considered present with a score ≥ 12 .

(6) Study Timeline

This study will take approximately one year to complete after IRB approval.

E. Adverse Event Criteria and Reporting Procedures

This is a minimal risk study. Any adverse effects associated with this study will be reported to the BCH IRB by the Principle Investigator (PI). If participants experience any adverse event related to this study and need follow-up for any concerns, they may be referred to the Patient Relations Department or Social Work Department at BCH as indicated.

F. Data Management Methods

All collected survey data as well as pre-op and PACU observation data will be de-identified and presented in aggregate, stored in REDCap® and kept in password-protected folders on BCH computers, accessible only by the research team members. The data collected directly from the PIRA program itself will be stored on a secure Northeastern University Server, and will be accessible only to the study team. Upon completion of data collection, the PIRA data will be transmitted back to BCH electronically and stored on the BCH server. All research team members will have completed CITI training.

G. Quality Control Method

Qualitative, free-text data will be analyzed by two or more members of the research team to ensure validity and concurrence of identified themes.

H. Data Analysis Plan

A Student's t-test will be used to compare the mean anxiety scores, mYPAS, between the groups. Free text entries from parents will be clarified, consolidated, and summarized by the research team for themes. Quantitative data from the parental preoperative survey will be summarized for mean, median, mode, and standard deviation and presented both numerically and graphically using Microsoft Excel.

I. Statistical Power and Sample Considerations

This pilot protocol is powered to see an effect on pediatric anxiety, as measured by the mYPAS. A sample size of 30 per group will provide 80% power to detect a difference of 6 in mean mYPAS scores between the two groups (assuming a standard deviation for the mYPAS of 8 based on published data in preoperative holding) (Kain et al., 1997), based on Student's t-test and assuming a two-tailed alpha level of 0.05. With a range of 22.5-100, prior studies (Kain et al., 1997) have used a reference score of 37 as consideration for high anxiety cases, with the

prevalence of such high-anxiety cases at 24%. Based on anticipated attrition of 20% due to failure to interact with the PIRA, potential for surgical or anesthesia cancellations before or on the day of surgery, or withdrawal from the study, a total of 76 patients (38 in each group) will be recruited.

J. Study Organization

This study will be directed by [name] and [name], DNP, CRNA with the support of other research team members at Boston Children's Hospital Waltham. The entire research team will be responsible for overseeing patient screening, recruitment and consent. Members of the research team will also be responsible for data collection, data analysis, as well as identifying and reporting adverse events.

Study team members at Northeastern University ([name], BA, PhD Student and [name], BSE, MS, PhD, Associate Dean of Research) were responsible for programming the PIRA and will be monitoring the tool for any technical issues and updating as needed.

Table 1. Outcomes

Outcome	Measurement	Scoring	Timing
Participant Demographics	Age of parent, Gender of parent who completed PIRA, Ethnicity	See Appendix B	Preoperative Waiting, self-reported.
Parental Utilization of PIRA (Primary)	Parental Survey	See Appendix B	Preoperative Waiting, self-reported.

Recommendation to Future Families (Primary)	Parental Survey	See Appendix B Sliding Scale (0 = Definitely NOT Recommended - 10 = Definitely Recommend)	Preoperative Waiting, self-reported.
Potential Gaps or Recommendations for Future Iterations (Primary)	Parental Survey, free text entry	See Appendix B Summarized for themes	Preoperative Waiting, self-reported.
Parental Anxiety (Secondary)	STAI	See Appendix B and Figure 2. Range 20-80, higher = greater anxiety	Preoperative Waiting, self-reported
Child Anxiety (Secondary)	mYPAS (Observational)	See Figure 1. Range 22.5-100	Preoperative Waiting, observed by a Research Assistant (RA)
Emergence from Anesthesia (ED) (Secondary)	PAED Scale (Observational)	See Figure 3. Range 0-20; Threshold for ED ≥ 12	PACU, observed by a Registered Nurse (RN) as per BCH standard of care.

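### The allocation rule as written does not guarantee 38 per group or balance the two surgical services; stratified permuted blocks would be a cheap improvement

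*Combined protocol and SAP*

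**What the plan says.** Section D(1) sets the ratio: "This study is a pilot 1:1 randomized trial with one control group and one intervention group". Section D(3) gives the whole of the allocation method: "Families that agree to participate in the study will be assigned a number (either one or two) from a random number generator". The documents mention no blocking, stratification, pre-generated list or concealment step.

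Section I gives the sample size: "A sample size of 30 per group will provide 80% power to detect a difference of 6 in mean mYPAS scores", "assuming a standard deviation for the mYPAS of 8" and "assuming a two-tailed alpha level of 0.05". It then allows for 20% attrition and concludes that "a total of 76 patients (38 in each group) will be recruited".

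Children come from two services, ORL and Urology (section D(2)); the expected split is not given. Section H compares mYPAS between groups with an unadjusted t-test.

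The primary outcomes concern the tool itself. Section D(4) says that "a primary outcome will evaluate whether families actually viewed the materials, with whom, and how much time they spent with the PIRA", and adds parents' impressions and willingness to recommend. Usage logs exist only for PIRA users. In Appendix B, parents who did not receive or view the tool are told to skip the recommendation and content-gap items.

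**The concern.** A separate draw of one or two for each family gives each an even chance of either arm, but does not fix how many land in each arm. The plan's 38 per group is then an expectation, not a property of the design.

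In most two-arm trials this hardly matters, because modest imbalance costs little power. Here one arm carries almost all the primary information: the number of PIRA families is in effect the sample size for utilisation, impressions and recommendation. At stake is protection against an unluckily small PIRA arm.

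The same rule does nothing to even out the surgical services. If service is related to anxiety or emergence behaviour, a visible chance difference in mix would add noise and be awkward to interpret, because no adjustment is planned.

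**Working it through.** **Inputs.** From section I: difference 6, SD 8, two-sided alpha 0.05, 30 evaluable per group, 20% attrition, 76 recruited. From D(1) and D(3): 1:1, one draw per family. Assumed, because the documents do not give them: independent draws, 80% use of the PIRA, and 15, 25 or 38 Urology children out of 76.

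**1. The plan's own figures.** The exact two-sample t calculation needs 29 per group for 80% power, and 30 per group gives 81.5%. Inflating for attrition: 30 / (1 − 0.20) = 37.5, rounded up to 38, total 76. The stated sample size is reproduced.

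**2. Arm sizes.** Let X be the number in the PIRA arm, X ~ Binomial(76, 0.5).
- P(X = 38) = 0.091
- P(30 ≤ X ≤ 46) = 0.950
- P(X ≤ 33) = 0.151
- P(X ≤ 30) = 0.042

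**3. PIRA completers at 20% attrition.**
- Independent draws: Binomial(76, 0.5 × 0.8 = 0.4), P(fewer than 25) = 0.082
- 38 fixed: Binomial(38, 0.8), P(fewer than 25) = 0.012

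**4. Precision of a primary proportion at 80% use.** Clopper-Pearson 95% limits:
- 30 families (24/30): 61% to 92%
- 38 families: 80% of 38 is 30.4, not a whole number. The limits are 63% to 90% at 30/38 and 66% to 92% at 31/38, so about 64% to 91% at 80%.

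The lower limit therefore moves about 2.5 points. With the normal half-width 1.96 × √(0.8 × 0.2 / n), a fixed 38 gives 12.72 points. The average over Binomial(76, 0.5) is 12.78, an expected loss of 0.06 points.

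**5. mYPAS power with 60 evaluable.** Exact t: 81.5% at 30:30, 80.8% at 26:34, 79.9% at 24:36, 78.6% at 22:38.

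**6. Service mix.** With each child allocated independently, the probability that the Urology share differs between arms by at least 15 points is:

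| Urology children of 76 (assumed) | P(difference ≥ 15 points) |
|---|---|
| 15 | 11% |
| 25 | 17% |
| 38 | 21% |

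Fixing 38:38 without strata leaves this at about 8% to 25% over the same range, so blocking alone does not deal with service mix.

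**7. Scale of a service imbalance.** Suppose, purely as an illustration, that the services differed by a full SD (8 points) on mYPAS. A 15-point imbalance would shift the group difference by 0.15 × 8 = 1.2 points. The standard error at 30 per group is 8 × √(2/30) = 2.07.

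**The case against.** The strongest reply is that the text is silent, not wrong. A restricted list produced with a random number generator would fit D(1), D(3) and section I together, and 38 per group can be read as a recruitment target. That stands: the documents do not rule out restriction, so the exact statement is that 38 per group is not guaranteed. The method still needs to be stated.

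Second, simple randomisation is valid, and a PIRA arm above 38 is as likely as one below it. That also stands. The average precision loss is negligible, and the primary outcomes have no precision target or success threshold to breach.

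Three stronger readings are tempting and are not supported:
- A reader might take the chance that either arm is small (30% for 33 or fewer, 8.5% for 30 or fewer) as the risk to the primary outcomes. Half of those trials have a large PIRA arm, which helps; the relevant figures are 15% and 4%.
- A reader might infer that the anxiety comparison is underpowered. The imbalances worked above cost about 1 to 3 points of power.
- A reader might infer that a chance difference in service mix biases mYPAS or PAED. Under randomisation it is part of the sampling error that the t-test already covers, and nothing in the documents shows that ORL and Urology children differ on either scale.

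Finally, stratified blocks do not secure exactly 38:38 either. That is true, but the departure is tightly bounded.

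**Conclusion.** The point holds as a cheap improvement of low to moderate severity. As written, the rule secures neither the planned arm sizes nor a similar service mix. The gain from restriction is protection against a bad draw: it cuts the chance of fewer than 25 PIRA completers from about 1 in 12 to about 1 in 80, and avoids a service imbalance that the planned analysis has no means of handling.

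This rests on reading D(3) as independent draws and on applying the plan's 20% attrition evenly across families. The precision figures assume 80% use. The service-mix figures depend on an assumed split, and they matter only if service is prognostic, which the documents do not establish.

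**What to change.** Replace the allocation sentence in D(3) with a statement along these lines: families are allocated 1:1 by permuted blocks of randomly varying size (for example 4 and 6), stratified by surgical service (ORL or Urology), from a list generated in advance and hidden from recruiting staff until the family is enrolled. REDCap could hold the list if its randomisation function is available; the documents mention REDCap only for surveys and data storage. In section H, include service as a covariate in the mYPAS comparison. If a restricted list already exists, describe it instead.

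With blocks of up to 6 in two strata, each stratum can end at most 3 apart, so the worst split of 76 is 35:41, against 30 to 46 in the PIRA arm as the 95% range now. The cost is a short amendment and one list. The downside is slightly more predictable allocation, which the varying block size limits.
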